4.2.3 Efficacy analysis

4.2.3.1 Estimands

Estimands for the study are defined in Table 2. Intercurrent events (IE) that may occur during the study are receipt of rescue therapy, IP discontinuation and study withdrawal.

Table 2 Estimand framework

Estimand	Attributes			Population-level summary
	Population	Variable	Intercurrent event strategy	
Primary	Evaluable	Change in HbA1c from baseline to Week 24	Rescue and IP discontinuation: Data after event excluded. Hypothetical approach due to missing at random (MAR) assumption of MMRM analysis. Withdrawal from study prior to Week 24: Hypothetical approach due to MAR assumption of MMRM analysis.	Least squares mean difference in CFBL at W24 between EQW and PBO
Sensitivity to primary	Evaluable	Change in HbA1c from baseline to Week 24	All IEs: Data after event excluded. Hypothetical approach using multiple imputation (MI) pattern mixture model imputation.	Least squares mean difference in CFBL at W24 between EQW and PBO

Supplementary to primary
	
Evaluable
	
Change in HbA1c from baseline to Week 24
	
Rescue and IP discontinuation: Data after event included. Treatment policy approach. Withdrawal from study prior to Week 24: Hypothetical approach due to MAR assumption of MMRM analysis.
	
Least squares mean difference in CFBL at W24 between EQW and PBO

Sensitivity to supplementary of primary
	
Evaluable
	
Change in HbA1c from baseline to Week 24
	
Rescue and IP discontinuation: Data after event included. Treatment policy approach. Withdrawal from study prior to Week 24: Hypothetical approach using MI pattern mixture model imputation.
	
Least squares mean difference in CFBL at W24 between EQW and PBO

Secondary 1
	
Evaluable
	
Change in HbA1c from baseline to Week 24 and each intermediate visit
	
Rescue and IP discontinuation: Data after event excluded. Hypothetical approach due to MAR assumption of MMRM analysis. Withdrawal from study prior to Week 24: Hypothetical approach due to MAR
	
Least squares mean difference in CFBL at Week 24 and each intermediate visit.

Secondary 2	Evaluable	Proportions of patients having HbA1c goals of <6.5%, ≤6.5% and <7.0% at Week 24 and at each intermediate visit	assumption of MMRM analysis. Rescue and IP discontinuation: Data after event excluded. Composite approach used, with patients with missing data at endpoint treated as non-responders. Withdrawal from study prior to Week 24: Composite approach used, with patients with missing data at endpoint treated as non-responders.	Difference in proportion of responders at Week 24 and each intermediate visit between EQW and PBO
Sensitivity to secondary 2	Evaluable	Proportions of patients having HbA1c goals of <6.5%, ≤6.5% and <7.0% at Week 24 and at each intermediate visit	Rescue and IP discontinuation: Data after event excluded. Hypothetical approach using MI pattern mixture model imputation. Withdrawal from study prior to Week 24: Hypothetical approach using MI pattern mixture model imputation.	Difference in proportion of responders at Week 24 and each intermediate visit between EQW and PBO
Other continuous secondary endpoints	ITT	Change in X from baseline to Week 24 and each intermediate visit	Rescue and IP discontinuation: Data after event excluded. Hypothetical approach due to MAR	Least squares mean difference in CFBL at Week 24 and each intermediate visit, as applicable.

				assumption of MMRM analysis. Withdrawal from study prior to Week 24: Hypothetical approach due to MAR assumption of MMRM analysis.	
Exploratory	Safety	Change in eGFR from baseline to Week 24 and each intermediate visit by baseline eGFR category	Rescue and IP discontinuation: Data after event excluded. Hypothetical approach due to MAR assumption of MMRM analysis. Withdrawal from study prior to Week 24: Hypothetical approach due to MAR assumption of MMRM analysis.	Least squares mean difference in CFBL at Week 24 and each intermediate visit.	
Sensitivity to exploratory	Safety	Change in eGFR from baseline to Week 24 and each intermediate visit by baseline eGFR category	Rescue: Data after event included. Treatment policy approach. IP discontinuation: Data after event excluded. Hypothetical approach due to MAR assumption of MMRM analysis.	Least squares mean difference in CFBL at Week 24 and each intermediate visit.	

				Withdrawal from study prior to Week 24: Hypothetical approach due to MAR assumption of MMRM analysis.	
--	--	--	--	-------------------------------------------------------------------------------------------------------	--

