1.3.1 Ethical safety considerations

Based on safety data from previous clinical studies of EQW (where the majority of patients had type 2 diabetes), development of small, asymptomatic, subcutaneous injection site nodules is expected. These nodules are usually transient and resolve without intervention. Injection site reactions were typically mild, transient, and did not interfere with therapy. Other risks with exenatide treatment include mild to moderate nausea, vomiting, and diarrhea.

Exenatide is a peptide and thus has the potential to elicit an allergic response. The Investigator will instruct patients to be aware of signs and symptoms that are consistent with an allergic response and to contact the Investigator immediately if such a response is suspected.

In patients using exenatide BID (BYETTA), there have been rare postmarketing reports of altered renal function, including increased serum creatinine, renal impairment, worsened chronic renal failure, and acute renal failure, sometimes requiring hemodialysis. Some of these events occurred in patients receiving 1 or more pharmacologic agents known to affect renal function/hydration status and/or in patients experiencing nausea, vomiting, and/or diarrhea, with or without dehydration.

Postmarketing cases of acute pancreatitis, including fatal and non-fatal hemorrhagic or necrotizing forms, have been reported in patients treated with BYETTA. In controlled clinical trials where exenatide (BID or once weekly) was studied in comparison to placebo or insulin, no differences in event rates for pancreatitis have been observed. Patients will be instructed to contact the Investigator or other healthcare provider if they experience persistent severe abdominal pain, with or without vomiting, because this is the hallmark symptom of acute pancreatitis. If pancreatitis is suspected, study medication should be discontinued. If pancreatitis is confirmed, appropriate treatment should be initiated and the patient should be carefully monitored until recovery. The Sponsor and Medical Monitor or Global Safety Physician should be contacted to discuss patient disposition.

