3.6.5.2 Safety and concomitant medications

Adverse events, hypoglycemic events and concomitant medications on the date of first dose of open-label EQW (Week 24 visit) will be assigned to the extension period as this is considered a conservative approach. Other safety assessments at the Week 24 visit will be considered to have been carried out pre-dose and will therefore be assigned to the controlled assessment period. This is reflected in the definitions below.

Controlled assessment period:

- For patients who do not enter the extension period, the controlled assessment period will be defined as date of first dose of randomized study medication to date of last dose of randomized study medication + 7 days (or + 90 days after last dose of study medication for reporting of serious adverse events (SAEs) and other clinically significant or related AEs).
- For patients who go on to enter the extension period, the controlled assessment period for all safety parameters except AEs, hypoglycemic events and concomitant medications will be defined as date of first dose of randomized study medication to date of first dose of open-label EQW. For AEs, hypoglycemic events and concomitant medications, the controlled assessment period will be defined as date of first dose of randomized study medication to date of the first dose of open-label EQW – 1 day, in order for AEs, hypoglycemic events and medications recorded on the date of first dose of open-label EQW to be assigned to the extension period.

Extension period: For all safety parameters, except AEs, hypoglycemic events and concomitant medications, the extension period will be defined as date of first dose of open-

label EQW + 1 to date of last dose of open-label EQW + 7 days. For AEs, hypoglycemic events and concomitant medications, the extension period will be defined as date of first dose of open-label EQW to date of last dose of open-label EQW + 7 days (or + 90 days for SAEs and other clinically significant or related AEs). The extension period will only be defined for patients who enter the extension period and receive at least one dose of open-label EQW.

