4.2.4 Safety and tolerability analysis

Analysis of safety data will be performed using the Safety analysis set. All safety and tolerability variables such as examination of AEs, clinical laboratory measurements, physical examination findings, vital signs, and antibodies to exenatide will be summarized descriptively by treatment groups. Observations post-rescue will be included for safety analyses.

For all safety endpoints summary tables will be presented by visit to Week 52, and where applicable also for the 10-week follow-up, for each treatment group. Continuous variables (observed, change from baseline, laboratory and vital signs parameters) will be summarized by visit using number, mean, median, standard deviation, minimum and maximum for each

treatment group. Categorical variables (incidence of AEs, antibodies, physical examination, Tanner pubertal stage) will be summarized by visit in the form of number and percentage (%) for each treatment group.

A listing of Tanner pubertal stage data will also be provided.

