A MMRM analysis of change in eGFR from baseline to Week 24 and each intermediate visit by baseline eGFR (hyperfiltrating: $\geq 125 \text{ ml/min/1.73m}^2$ versus non-hyperfiltrating: $< 125 \text{ ml/min/1.73m}^2$) will be provided. The same approach as stated in Section 4.2.3.3 will be used. The model will include treatment group, visit, interaction between visit and treatment, region, screening HbA1c strata ($< 9.0\%$, $\geq 9.0\%$), baseline eGFR, and interaction between visit and baseline eGFR as the fixed effects. The REML method will be used for parameter estimation. The least squares mean, 2-sided 95% confidence interval, and p-value of the difference in the endpoints of interests between the EQW and PBO groups will be presented. This analysis will be done both excluding data after initiation of rescue therapy and separately including data after initiation of rescue therapy.

A shift table from baseline UACR category to highest post-baseline UACR category will be provided for the controlled assessment period and extension period, separately. Categories are defined as follows:

- $< 30 \text{ mg/g}$ (Normal)
- $\geq 30 \text{ mg/g}$ and $\leq 300 \text{ mg/g}$ (Micro or moderately increased albuminuria)
- $> 300 \text{ mg/g}$ (Macro or severely increased albuminuria)
- Unknown

Strip Sign for Selected Laboratory Data

For selected laboratory test values that have been received with a qualifier as a part of the result ($>$, \geq , $<$, or \leq), a process to strip the qualifier will be applied and the resulting numeric

values will be used for data analysis. The raw value with operator will remain as such in the database and will be used when listed.

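### Neither planned eGFR model tests the missing-at-random assumption for patients who stop study drug; the row labelled sensitivity varies rescue handling only

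*SAP*

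**What the plan says.** SAP Table 2 has two eGFR rows in the Safety set, both for this variable: "Change in eGFR from baseline to Week 24 and each intermediate visit by baseline eGFR category".

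- The Exploratory row says: "Rescue and IP discontinuation: Data after event excluded. Hypothetical approach due to MAR assumption of MMRM analysis".
- The Sensitivity to exploratory row says: "Rescue: Data after event included. Treatment policy approach. IP discontinuation: Data after event excluded". It then gives the same missing-at-random rationale for stopping.

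The methods text in SAP 4.2.4.4 describes the same pair: "This analysis will be done both excluding data after initiation of rescue therapy and separately including data after initiation of rescue therapy". It does not mention stopping study drug, but it points to the primary analysis: "The same approach as stated in Section 4.2.3.3 will be used". Section 4.2.3.3 keeps values up to and including the date of stopping.

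Protocol 1.3.1 records, for exenatide BID, that "there have been rare postmarketing reports of altered renal function, including increased serum creatinine, renal impairment", among other renal events. SAP section 5 explains that eGFR is not a protocol endpoint and that the team added it as important information.

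**The concern.** For an efficacy measure it can be reasonable to ask what would have happened had the patient stayed on drug. For a safety measure, the reason for stopping may be the harm itself. Missing at random then supplies a later course based on the patient's own earlier values and on patients in the same arm who continued. If the fall has not yet been seen in the retained values, that course is too favourable.

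A row labelled sensitivity should vary the assumption most open to doubt. Here it varies rescue and leaves stopping unchanged. HbA1c is treated more fully in the same SAP: Table 2 has a Supplementary to primary row that includes data after stopping under treatment policy, and 4.2.3.4 adds a placebo-based missing-not-at-random analysis. eGFR has neither. The two eGFR models are the only inferential comparison of kidney function between arms.

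**Working it through.** **When chemistry is drawn.** In Protocol 6.2.3, post-baseline chemistry in the controlled period is listed at Week 12 (6.2.3.4), Week 24 (6.2.3.7) and Early Termination (6.2.3.10). It is not listed at Weeks 4 and 8 (6.2.3.3) or Week 18 (6.2.3.6). For a patient who stops between draws, the Early Termination sample may be the first to show a fall.

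**Which values the models can use.**
- SAP 4.2.3.3: values on or before the stop date are kept and later ones excluded.
- SAP Table 3.8: the Week 12 window is Day 71-126. Week 24 runs from Day 127 to the last day of the controlled period. Days 2-70 have no window.
- SAP 4.3.4.1: if a window holds several values, the one nearest the target day is used. A value from, say, Day 110 gives way to one from Day 85 even if both are eligible.
- SAP 3.6.5.2: for patients who do not enter the extension, the safety period ends at "date of last dose of randomized study medication + 7 days".

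**Size, as an illustration.** The documents give no eGFR variance, event rate or size of fall, so there is no planned figure to reproduce. Inputs:
- EQW patients: 77 x 5/7 = 55 (Protocol 12.7).
- Assumed: k = 5 stoppers (5/55 = 9.1%), a lasting fall d of 20 or 40 mL/min/1.73 m², correlation r between Weeks 12 and 24 of 0.5 to 0.9, and equal SDs at the two visits.

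The shift in the EQW Week 24 mean if every value counted is (k/55) x d: 5 x 20/55 = 1.8, or 5 x 40/55 = 3.6. The shift that the planned models retain depends on when the fall is measured. In case B the model implies a Week 24 fall of r x d.

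| Case | Retained, d = 20 | Retained, d = 40 |
|---|---|---|
| A. Stop before Day 71, no windowed post-baseline value | 0 | 0 |
| B. Fall measured at Week 12 on or before the stop; Week 24 excluded | -0.9 / -1.3 / -1.6 for r = 0.5 / 0.7 / 0.9 | -1.8 / -2.5 / -3.3 |
| C. Week 12 value precedes the fall, which is first seen after the stop | 0 | 0 |
| D. Fall measured on or before the stop, Day 127 or later | -1.8 (all) | -3.6 (all) |

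The loss is complete in A and C, 10% to 50% in B, and nil in D. For 5% to 15% of patients and falls of 20 to 40, the loss in A and C runs from 0.05 x 20 = 1.0 to 0.15 x 40 = 6.0. With fewer patients and other falls, it runs from 2 x 30/55 = 1.1 to 3 x 70/55 = 3.8. The analysis is by baseline eGFR category, so a shift within a category would be larger: 2 x 50/27 = 3.7 if a category held 27 EQW patients (assumed).

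**What an added row would recover.** A post-stop value mapped to Week 12 moves case A to case B. One mapped to Week 24 moves case C to case D.

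**The case against.** The strongest reply is that a reader might infer that any renal decline leading to stopping is replaced by the course of patients who tolerated the drug. The documents do not support that. Values up to and including the stop date are kept, and they inform the implied later course. SAP 4.1.3.4 places Early Termination procedures at the time of study discontinuation, and a sample on the stop date is retained. A decline that itself prompts stopping may well have been measured first: investigators may order laboratory tests (Protocol 1.3.1) and must follow up significant abnormalities (6.4.5). Nothing shows that the Early Termination creatinine is usually the only value revealing a fall. All of this stands and limits the point to cases A and C, part of B, and values displaced by the nearest-to-target rule.

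A reader might also take these models as the only renal comparison between arms. They are only the only inferential one. SAP 4.2.4.4 plans observed and change-from-baseline eGFR, chemistry summaries with minimum and maximum shift tables, and a UACR shift table. SAP 4.2.4.1 reports events leading to study discontinuation whatever their date. A serious renal event would appear there.

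An on-treatment estimand is a legitimate choice for an exploratory measure. The SAP 4.2.4 statement "Observations post-rescue will be included for safety analyses" concerns rescue, so it does not settle how stopping should be handled. Neither reply gives the existing sensitivity row any power to test the assumption about stopping.

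**Conclusion.** Both eGFR models exclude values after stopping study drug under missing at random, and neither tests that assumption. A fall first measured after the stop date is lost from both. Where it is harmful and caused the stop, the EQW-placebo difference is biased towards no harm.

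It would be too strong to say that both models are biased towards no harm in general. The loss depends on timing, and in a patient hyperfiltrating at baseline (125 mL/min/1.73 m² or above) a fall may not be harm, so the direction is not fixed. The size is unknown. The figures of 1.0 to 6.0 rest on assumed shares and falls, complete loss of the relevant values, and no matching loss on placebo. Protocol 1.3.1 calls the renal reports rare, so the lower end is the more likely.

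The point is worth acting on because the harm is named, the samples are already collected, and Protocol 1.1 describes release from the microspheres over days to months, so an early post-stop value may still reflect exposure. It does not threaten the primary conclusion.

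**What to change.** Add one row to Table 2, and a matching sentence in 4.2.4.4, for a supplementary eGFR model that handles both rescue and stopping study drug by treatment policy, parallel to the HbA1c Supplementary to primary row. The row needs its own rules, because the existing ones would defeat it:

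- **Cut-off:** include all collected values through Day 169 regardless of last dose, including Early Termination. A Week 24 visit falling later within the two-day visit tolerance should also count. Exclude values taken after the first open-label dose. This overrides the last-dose-plus-7-days limit for this analysis only.
- **Early values:** map Days 2-70 to Week 12, since Table 3.8 has no window for them.
- **Shared windows:** say what happens when an Early Termination value and a scheduled Week 12 value fall in the same window, because the nearest-to-target rule could discard the former. SAP 4.2.3.5 already maps Early Termination values to a scheduled visit for secondary variables and is a precedent.

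Report the row beside the two existing ones, not in place of them, and list eGFR for every patient who stops study drug.

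The cost is one more model run, a few lines of text and a listing, with no new data. The added row mixes on-drug and off-drug values. It recovers mainly the Early Termination sample, because the Extended Safety Follow-up (Protocol Appendix E) collects no chemistry, and it still relies on missing at random after a patient's last sample.

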4.2.3.2 Hierarchical testing strategy

To protect the family-wise error rate for the primary endpoint and secondary endpoints, a fixed sequence procedure hierarchical testing strategy will be followed i.e., only if superiority for the primary endpoint is established at the significance level $\alpha = 0.05$ two-sided, the superiority test for the selected secondary endpoints will be tested in the order specified, also at the significance level $\alpha = 0.05$ two-sided. Endpoints will be tested in the following order:

1. Change in HbA1c from baseline Visit 2 (Week 0) to Visit 7 (Week 24).
2. Change in fasting plasma glucose concentration from baseline Visit 2 (Week 0) to Visit 7 (Week 24)
3. Change in body weight from baseline Visit 2 (Week 0) to Visit 7 (Week 24)
4. Change in fasting insulin from baseline Visit 2 (Week 0) to Visit 7 (Week 24)

If the null hypothesis is not rejected for any of the first four tests in the hierarchy, for remaining endpoints a p-value will be presented in outputs but will be considered exploratory and inferences will not be drawn.

For all other secondary and exploratory endpoints, p-values will be presented but these will be considered exploratory in nature with no multiplicity adjustment applied. A nominal level of $\alpha = 0.05$ will be used for inference.

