3.6.2 Change and percent change from baseline

Change from baseline to any randomized treatment period Week t is defined as follows:

$$C_{Week\ t} = M_{Week\ t} - M_{baseline},$$

Where:

- $C_{Week\ t}$ is the change from baseline at Week t ,
- $M_{Week\ t}$ is the measurement at Week t ,

- $M_{baseline}$ is the baseline measurement.

Percent change from baseline to any randomized treatment period Week t is defined as follows:

$$P_{Week\ t} = 100 \times (M_{Week\ t} - M_{baseline}) / M_{baseline}.$$

If the baseline value is zero, the percent change will be missing.

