4.1.5 Statistical modelling

In general, continuous variables will be analyzed using a MMRM if multiple post-baseline measurements are required by CSP. The MMRM analysis will be treated as the primary analysis method for continuous efficacy endpoints. The statistical analysis of categorical variables will be done using a stratified Cochran-Mantel-Haenszel (CMH) test.

Standard diagnostic approaches will be used to verify that the key statistical assumptions of the MMRM and CMH test hold.

If the distributional assumptions of the MMRM for the primary analysis do not hold, alternative models will be explored using appropriate transformed data.

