4.2.3.5 Analysis of secondary variables

Summary statistics and frequency tables will be provided for all secondary endpoints by visit and treatment for the ITT analysis set during the controlled assessment period and separately for the subset of ITT patients who received open-label EQW during the extension period for the Treatment period (see Section 3.6.5 for Treatment period definition), unless otherwise stated.

Similar to the primary analysis, data including the Early Termination visit where applicable will be included in the MMRM and CMH analysis for secondary analysis variables. Data collected from an Early Termination visit will be mapped to the next closest scheduled visit. For patients who initiate rescue medication and continue study participation, data collected after the initiation of rescue medication will be excluded from analyses. Data collected after discontinuation of IP will be excluded from analyses for all secondary efficacy endpoints.

Change in HbA1c from baseline Visit 2 (Week 0) to Visit 10 (Week 52), and to each intermediate visit as applicable

The MMRM method for change in HbA1c will be used until Week 24 and to each intermediate visit, using the Evaluable analysis set, which is the same approach as stated in Section 4.2.3.3.

The least squares mean (LSM) change from baseline and SE bar by visit will be presented in a figure by treatment group. The p-value for the difference between treatment groups by visit will also be provided in the figure.

The observed values and change from baseline will be summarized by visit using descriptive statistics (mean, median, standard deviation, minimum, maximum). This will be provided separately for both the Evaluable analysis set during the controlled assessment period and for the subset of Evaluable patients who received open-label EQW during the extension period analysis set for the Treatment period.

HbA1c measures will be listed.

Change in fasting plasma glucose concentration, body weight, fasting insulin, lipids, blood pressure from baseline Visit 2 (Week 0) to Visit 7 (Week 24), Visit 10 (Week 52), and to each intermediate visit as applicable

The same MMRM approach will be used to analyze the change in body weight, blood pressure, fasting plasma glucose, and fasting insulin from baseline (Week 0) to Week 24, and each intermediate visit.

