The least squares mean (LSM) change from baseline and SE bar by visit will be presented in a figure by treatment group. The p-value for the difference between treatment groups by visit will also be provided in the figure.

The observed values and change from baseline will be summarized by visit using descriptive statistics (mean, median, standard deviation, minimum, maximum) for body weight, blood pressure, fasting plasma glucose, fasting insulin and lipids. This will be provided separately for both the ITT analysis set during the controlled assessment period and for the subset of ITT patients who received open-label EQW during the extension period for the Treatment period.

The models for changes in body weight, blood pressure, fasting plasma glucose, and fasting insulin will include treatment group, visit, interaction between visit and treatment, region, baseline of the dependent variable, interaction between visit and baseline of the dependent variable and screening HbA1c strata ($<9.0\%$, $\geq 9.0\%$) as the fixed effects. The REML method will be used for parameter estimation. The least squares mean, 2-sided 95% confidence interval, and p-value of the difference in the endpoints of interests between the EQW and PBO groups will be provided.

FPG, body weight, fasting insulin, lipids and blood pressure (systolic and diastolic) will be presented in listings.

Proportions of patients achieving HbA1c goals at Visit 7 (Week 24), Visit 10 (Week 52), and at each intermediate visit

Proportions of patients having HbA1c goals of $<6.5\%$, $\leq 6.5\%$ and $<7.0\%$ at Week 24 and at each intermediate visit will be compared between treatments using the Evaluable analysis set via the CMH procedure, in which screening HbA1c strata ($<9.0\%$, $\geq 9.0\%$) will serve as the stratification factors.

A bar chart of the percentage of patients achieving HbA1c goals of $<6.5\%$, $\leq 6.5\%$ and $<7.0\%$ by visit and treatment group will be provided along with p-values.

Any Evaluable patient without HbA1c value at the endpoint will be considered as not achieving HbA1c goal at endpoint. The denominator will be the total number of Evaluable patients in a treatment group, and the numerator will be the number of patients achieving HbA1c $<6.5\%$, $\leq 6.5\%$ and $<7.0\%$.

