Change in beta-cell function (HOMA-B) and insulin sensitivity (HOMA-S) as measured by homeostasis model assessments in patients not taking insulin from baseline Visit 2 (Week 0) to Visit 7 (Week 24), Visit 10 (Week 52), and to each intermediate visit as applicable

The same MMRM approach will be used to analyze the change in beta-cell function (HOMA-B) and insulin sensitivity (HOMA-S) as measured by homeostasis model assessments in patients not taking insulin from baseline Visit 2 (Week 0) to Week 24, and each intermediate visit.

The least squares mean (LSM) change from baseline and SE bar by visit will be presented in a figure by treatment group. The p-value for the difference between treatment groups by visit will also be provided in the figure.

The observed values and change from baseline for these parameters will be summarized by visit using descriptive statistics (mean, median, standard deviation, minimum, maximum). This will be provided separately for both the ITT analysis set during the controlled assessment period and for the subset of ITT patients who received open-label EQW during the extension period for the Treatment period.

The effects of the study medications on HOMA will be examined. The pancreatic beta-cell function (HOMA-B) and peripheral and hepatic insulin sensitivity (HOMA-S) will be computed from a computerized HOMA model, which can predict the plasma glucose, insulin, c-peptide, and proinsulin concentrations for any possible combination of these 2 parameters in the fasting state in patients not taking insulin.

HOMA-B and HOMA-S will be computed from a computerized HOMA model, the HOMA Calculator². The HOMA Calculator, developed by Diabetes Trials Unit at the Oxford Center for Diabetes, Endocrinology, and Metabolism, is a computer algorithm that takes account of variations in hepatic and peripheral glucose resistance, increases in the insulin secretion curve for plasma glucose concentrations above 10 mmol/L (180 mg/dL), and the contribution of circulating proinsulin (e.g., C-peptide) to estimate the steady state beta-cell function and insulin sensitivity, as percentages of a normal reference population. The model assumes %HOMA-B and %HOMA-S values of 100% in normal young adults as a recalibration.

All HOMA parameters will be analyzed on a logarithmic scale (natural logarithmic transformation), and then back-transformed to the original scale for result presentation using the following formulae:

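### Does testing fasting insulin untransformed, with no stated fallback for skewed data, weaken the last alpha-controlled test?

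*SAP*

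**What the plan says.** SAP section 4.2.3.2 lists four tests in fixed order: HbA1c, fasting plasma glucose, body weight and fasting insulin, all at Week 24. The fourth entry reads "Change in fasting insulin from baseline Visit 2 (Week 0) to Visit 7 (Week 24". Every other endpoint is exploratory. Insulin is therefore a confirmatory test, and no protected test comes after it.

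The analysis is in section 4.2.3.5: "The same MMRM approach will be used to analyze the change in body weight, blood pressure, fasting plasma glucose, and fasting insulin from baseline". The terms of the model are then listed ("The models for changes in body weight, blood pressure, fasting plasma glucose, and fasting insulin will include treatment group, visit" and so on). Section 3.6.2 ("Change from baseline to any randomized treatment period Week t is defined as follows") sets change as the visit value minus the baseline value. Table 2 in section 4.2.3.1 gives the summary for these endpoints as "Least squares mean difference in CFBL at Week 24 and each intermediate visit, as applicable". No transformation is named for insulin.

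Section 4.1.5 promises checks in general terms: "Standard diagnostic approaches will be used to verify that the key statistical assumptions of the MMRM and CMH test hold". Its remedy is worded more narrowly: "If the distributional assumptions of the MMRM for the primary analysis do not hold, alternative models will be explored using appropriate transformed data".

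For the HOMA indices, section 4.2.3.5 does name a scale: "All HOMA parameters will be analyzed on a logarithmic scale (natural logarithmic transformation), and then back-transformed to the original scale".

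**The concern.** Three things make this look like an oversight. First, insulin concentrations may well be right-skewed, and the SAP already takes logs for HOMA-B and HOMA-S, which are computed from fasting values. Second, section 4.1.5 plans a check for every MMRM but states a response only for the primary one, so a protected test appears to have a diagnostic with no consequence. Third, the arms are small and unequal (at least 50 and 20 evaluable patients), so a few large values could inflate the standard error.

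If the raw scale were clearly the weaker one, the trial would be giving up power on a controlled test for want of a line of SAP text. If someone later changed the scale after seeing unblinded data, the result would lose its confirmatory standing.

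**Working it through.** **1. Is the scale left open?** Set the sections side by side.

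| Element | SAP section | What it fixes |
|---|---|---|
| Change | 3.6.2 | A difference, visit minus baseline |
| Summary measure | 4.2.3.1, Table 2 | LS mean difference |
| Model terms, REML | 4.2.3.5 | Untransformed change, baseline of the same variable |
| Transformed-data fallback | 4.1.5 | Named for the primary analysis |

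On this reading nothing in the SAP permits another scale for insulin, so no choice remains to be made after unblinding. Analysis and estimand also agree: a mean difference is defined and a mean difference is tested.

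**2. The plan's own figure.** Section 1.3 gives 74% power for HbA1c with a difference of 0.7, SD 1.0 and 70 patients. The standard error is 1.0 × √(1/50 + 1/20) = 0.2646, and 0.7 / 0.2646 = 2.646. A two-sided 5% t test with 68 degrees of freedom then has 74.2% power, which reproduces the figure. The documents state no SD, correlation or effect for insulin, so everything below is assumed.

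**3. Validity.** Under log-normal insulin (log-SD 0.4 to 1.0), simulated type I error of the raw-change analysis is 4.4% to 4.9%.

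**4. Power.** The stand-in for the MMRM is an ANCOVA at Week 24 with 50 versus 20 patients, two-sided 5%, without region or strata terms. The raw analysis regresses Y − X on treatment and X. The log analysis regresses log Y − log X on treatment and log X. For a gamma distribution with shape k, CV = 1/√k and skewness = 2/√k, so k = 1.5, 2 and 3 give CV 82%, 71% and 58% and skewness 1.6, 1.4 and 1.2.

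| Assumed insulin | Assumed effect | Correlation | Raw % | Log % | Raw − log |
|---|---|---|---|---|---|
| Log-normal, CV 50% | × 0.7 | 0.6 | 91.5 | 93.9 | −2.4 |
| Log-normal, CV 80% | × 0.7 | 0.6 | 55.7 | 65.2 | −9.5 |
| Log-normal, CV 80% | × 1.4 | 0.6 | 42.1 | 60.7 | −18.6 |
| Log-normal, CV 100% | × 1.4 | 0.6 | 26.7 | 45.7 | −19.0 |
| Log-normal, CV 80% | + 0.4 median | 0.6 | 47.5 | 85.2 | −37.7 |
| Gamma, k = 2 | + 0.25 mean | 0.5 | 33.2 | 61.6 | −28.4 |
| Gamma, k = 1.5 | × 0.7 | 0.6 | 53.1 | 40.3 | +12.8 |
| Gamma, k = 2 | × 0.7 | 0.5 | 59.6 | 49.3 | +10.3 |
| Gamma, k = 3 | × 0.7 | 0.5 | 76.3 | 68.1 | +8.2 |
| Gamma, k = 2 | × 1.4 | 0.5 | 45.2 | 43.9 | +1.3 |
| Log-normal, CV 80% | 70% cut of the excess over the median | 0.6 | 57.1 | 29.3 | +27.8 |
| Normal, CV 30% | − 0.7 SD | 0.6 | 90.0 | 82.3 | +7.7 |

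Right skew with a proportional effect does not by itself favour the log scale. It does under log-normal skew. Under gamma skew with a proportional decrease, the log scale is the weaker one.

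**5. Would a blinded rule settle it?** Take the natural candidate: use logs if the pooled, blinded Week 0 skewness exceeds 1. Its size is sound (4.6% to 5.2%). At log-normal CV 80% it raises power from 55.7% to 64.9% (× 0.7) and from 42.1% to 59.8% (× 1.4). But it selects logs in about 82%, 68% and 47% of gamma samples (k = 1.5, 2, 3) and loses 4 to 10 points against the existing plan at × 0.7 with correlation 0.6. For the effect concentrated in high values, power falls from 57% to 31%. At log-normal CV 50% it picks logs in 69% to 70% of samples, so sampling chance would decide whether the confirmatory test estimates a mean difference or a ratio.

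**6. Reaching the test.** Insulin is tested only if HbA1c, glucose and weight all succeed. Taking test 1 alone, and outcomes as independent, the largest proportional-effect loss in the table becomes 0.74 × 19.0 = 14.1 points, and the largest constant-shift loss 0.74 × 37.7 = 27.9 points.

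**The case for a change.** The strongest opposing case does not need the log scale to be better. It says that a protected test with a planned assumption check should have a planned response, whichever scale is preferred, and that one sentence would supply it. The wording of section 4.1.5 is indeed uneven. The same section calls the MMRM the primary method for continuous efficacy endpoints, so the fallback could be read to cover insulin too. Section 4.2.3.3, which reserves the term primary analysis for the HbA1c model, supports the narrower reading adopted here. On the broad reading the supposed gap disappears. On the narrow one, the response to a failed diagnostic is to keep the pre-specified analysis, which is legitimate when its type I error holds.

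It also stands that the raw scale loses badly if treatment shifts skewed insulin by a roughly constant amount, under log-normal and gamma skew alike. Nothing in the documents says that the effect takes this form.

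The HOMA comparison carries little weight. Those are derived indices, restricted to patients not taking insulin and outside the hierarchy. The fasting insulin test uses the ITT set, which can include insulin-treated patients. Logging HOMA shows that the method is available, and says nothing about how measured insulin is distributed.

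**Conclusion.** The concern does not hold. The documentary observations are right: insulin is the last of four controlled tests, it is analysed untransformed, and the fallback most naturally concerns HbA1c only. What follows from them is a fully specified test with sound type I error that matches its estimand, leaves no scale to be chosen after unblinding and blocks no later test.

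The power argument has no established sign. In the scenarios tabulated, the raw scale runs from 37.7 points worse to 27.8 points better than the log scale, and right skew with a proportional effect falls on both sides. These figures rest on assumed distributions, correlations of 0.5 to 0.6, complete data and a single-visit ANCOVA. The documents supply none of the insulin inputs. Moving to logs would also replace the mean difference of Table 2 with a ratio of geometric means. A sponsor could reasonably have chosen either scale, and keeping the raw one is neither an error nor a clear loss.
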